## 8.2 EXCLUSION CRITERIA

Note: All criteria apply to each eye

- Irregular corneal astigmatism
- Any corneal pathology/abnormality other than regular corneal astigmatism
- Previous corneal surgery
- Recent ocular trauma or intraocular surgery that is not resolved/stable or may affect visual outcomes
- Any pupil abnormalities (non-reactive, fixed pupils, or abnormally shaped pupils)
- Subjects with conditions associated with increased risk of zonular rupture, including capsular or zonular abnormalities that may lead to IOL decentration, including pseudoexfoliation, trauma, or posterior capsule defects
- Known ocular disease or pathology that may affect visual acuity or that may require surgical intervention during the course of the study (macular degeneration, cystoid macular edema, diabetic retinopathy, uncontrolled glaucoma, etc.)
- Concurrent participation or participation during 30 days prior to preoperative visit in any other clinical study
- Planned monovision correction
- Patient is pregnant, plans to become pregnant, is lactating or has another condition associated with the fluctuation of hormones that could lead to refractive changes

## 9. INVESTIGATOR SELECTION

### 9.1 INVESTIGATOR QUALIFICATIONS

AMO will select ophthalmic surgeons who have completed a residency in ophthalmology (or its documented equivalent), and are licensed to practice medicine and perform surgery at his/her investigative site. Each site will have one designated principal investigator; some sites may have additional implanting sub-investigators/surgeons.

Investigators will be selected from surgeons who are experienced in small-incision, phacoemulsification and toric IOL implantation in cataract patients. Additionally, investigators should have established their personalized A-constant for the TECNIS Toric ZCT. All sites are required to have adequate staff support for reporting and subject follow-up, as well as the necessary instrumentation to conduct study testing.

### 9.2 INVESTIGATOR OBLIGATIONS

Investigators are required to fulfill the following obligations:

- Conduct the study in accordance with the relevant and current protocol. Investigator will only make changes to a protocol after notifying and obtaining approval from AMO, the FDA or other governing agencies, and the Institutional Review Board (IRB), except when necessary to protect the safety, rights or welfare of subjects
- Personally conduct and supervise the study
- Maintain a list of appropriately qualified persons to whom the investigator has delegated significant trial-related duties
- Be responsible for protecting the rights, safety and welfare of subjects under the investigator's care and be responsible for the control and documentation of the devices under investigation
- Inform patients that the device(s) are being used for regulatory post-approval purposes and that requirements relating to obtaining informed consent and IRB approval are met according to 21CFR50, 21CFR56, 21CFR812 and all other applicable laws and regulations
- Maintain confidentiality as required by HIPAA or similar laws and regulations
- Shall not obtain written informed consent from any subject to participate or allow any subject to participate before obtaining FDA and IRB approval
- Document in each subject's case history that informed consent was obtained prior to participation in the study as required by 21CFR812
- Report to AMO and the reviewing IRB any adverse experiences that occur during the course of the study in accordance with applicable laws and regulations
- Maintain adequate and accurate records in accordance with applicable laws and regulations and make available all study documents and subject medical records for inspection by either AMO, duly authorized regulatory agencies (e.g., FDA) and/or the IRB

- Submit progress reports on the investigation to AMO and the reviewing IRB at regular intervals, but no less often than yearly as required by 21CFR812.150
- Ensure the IRB that is responsible for initial and continuing review of the study complies with applicable laws and regulations
- Report all changes in research activity and all unanticipated problems involving risks to patients to the IRB and AMO
- Provide sufficient accurate financial information to AMO to allow AMO to submit complete and accurate certification or disclosure statements as required by 21CFR54. Promptly update this information if any relevant changes occur during the course of the study or for up to one year following completion of the study
- Comply with all other obligations of clinical investigators and requirements according to all applicable FDA regulations (e.g., 21CFR812), all other applicable laws and regulations, and all conditions of approval imposed by the reviewing IRB, the FDA and the regulatory agency of the country in which the study is being conducted
- Ensure that all associates, colleagues and employees assisting in the conduct of the study are adequately informed about the protocol, the study device, their study-related duties and functions and agree to fulfill their obligations in meeting the above commitments.

Investigators shall provide adequate time and resources to conduct and report on the study. The Investigator, or delegate, shall notify AMO of any change in the conduct of the study including changes in study personnel assigned to the study project, location of the study device(s), or maintenance of study records, etc.

### **9.3 INVESTIGATOR APPROVAL**

It is the responsibility of the investigator to obtain prospective approval of the study protocol, protocol amendments or changes, informed consent forms and other relevant documents (e.g., advertisements) from the IRB. All correspondence with the IRB should be retained in the Investigator Study Files/Notebook. Copies of IRB submissions and approvals should be forwarded to AMO. Study sites will obtain IRB approvals and fulfill any other site-specific regulatory requirements. The investigator is required to report to AMO within five working days any withdrawal of approval by the reviewing IRB for his/her participation in the investigation.

Prior to the start of subject enrollment, the following documents must be signed and returned to AMO:

- Confidentiality Agreement
- Clinical Trial Agreement
- Investigator Agreement/Protocol Signature page
- Financial Disclosure form
- Signed and dated copy of investigator's current curriculum vitae
- Copy of the investigator's current medical license

- Hospital/Ambulatory Surgery Center Clinical Study Acknowledgement, if required

By signing the study documents, the investigator agrees to conduct this study according to the obligations above and all other applicable regulatory and legal requirements.

## 10. STUDY TIMELINE

This study will be initiated following the USA FDA approval of the TECNIS Toric IOL, Models ZCT450, ZCT525, and ZCT600 for the correction of aphakia and pre-existing corneal astigmatism of three diopters or greater (P980040/S058) and FDA approval of this protocol. The expected study timeline is presented in **Table 3**.

**TABLE 3**  
**Expected Study Timeline**

Study Activity	Expected Timing
Begin IRB approvals, site initiations and subject enrollment	JAN 2016: Following FDA approval of Post-Approval Study protocol and PMA approval of TECNIS Toric IOL Models ZCT 450, ZCT525 and ZCT600
Complete Site IRB approvals and initiations for initial 10 sites	JUL 2016: 6 months (~1-2 sites/month)
Complete Site IRB approval and initiations for additional sites	JUN 2017
Complete subject enrollment	SEP 2018: (~1 subject/site/3 months)
Complete subject follow-up	APR 2019: 6 months NOV 2019: 12 months a
Complete primary-analysis, 6-month clinical study report	JUL 2019: 3 months following completion of 6-month exams
Complete 1-year clinical study report	FEB 2020: 3 months following completion of 1-year exams

a An additional 6 months may be necessary depending upon the number and timing of subjects returning for 1 year visits (due to reports of severe visual distortions at 6 months or the occurrence of an IOL repositioning procedure)

Additionally, AMO will provide interim study reports every 6 months for the first two years following FDA approval of the lens models (July 31, 2015) and then annually thereafter until completion of the post-approval study. Further details on interim reports are provided in Section 20.5 Interim Reports.

## 11. STUDY PLAN

### 11.1 OVERVIEW

This study will be conducted in accordance with U.S. Code of Federal Regulations, the Declaration of Helsinki, ISO 14155 and all other applicable laws and regulations. The study will not begin until regulatory and IRB approvals have been obtained

This study is a prospective, multicenter, bilateral, non-randomized, open-label, clinical study conducted at up to 20 US sites. Subjects will be bilaterally implanted with high cylinder TECNIS Toric IOLs, Models ZCT300-ZCT600 in both eyes with at least one eye implanted with a Model ZCT450, ZCT525 or ZCT600. The eye with the highest toric power lens will determine the lens group. Second-eye surgeries are to be performed within approximately 1 month (no more than 60 days) of the first-eye surgery, as second-eye cataract surgeries are typically performed within 2 months of the first-eye surgery. Subjects will be examined postoperatively at 1 and 6 months following the second-eye surgery. If a subject requires a lens repositioning procedure due to IOL misalignment or if a subject reports a severe visual distortion at 6 months, the subject will undergo a final visit at 1 year. Additional visit schedule details are provided in Section 11.2 Visit Schedule.

At the 1-month visit, a spectacle and/or contact lens prescription will be offered to each subject. Postoperative procedures will include uncorrected and best corrected visual acuities, manifest refraction, intraocular pressure and biomicroscopic slit-lamp examination. In addition, if the subject has a spontaneous report of any of the 5 visual distortion items of interest or of blurred or hazy vision, the questionnaire will be administered and keratometry and toric IOL axis measurements will be performed.

At the 6-month visit, the postoperative procedures will include a subject questionnaire for determination of visual distortions, keratometry, uncorrected and best corrected visual acuities, manifest refraction, intraocular pressure and a biomicroscopic slit-lamp examination for determination of toric IOL axis position and for any adverse events.

If outside of a scheduled study visit, a subject has a spontaneous report of; 1) any of the 5 visual distortion items of interest or 2) blurred or hazy vision at one month postoperatively or later, the PRVDQ questionnaire will be administered and keratometry and toric IOL axis measurements will be performed. Exam details will be documented on an unscheduled visit form.

If a subject reported a severe visual distortion in the questionnaire or experienced a serious or device-related adverse event at any unscheduled study visit, uncorrected distance visual acuity, best corrected distance visual acuity, manifest refraction, keratometry, intraocular pressure and biomicroscopic slit-lamp examinations will also be performed.

A 1-year examination will be required only if the subject reports a severe visual distortion at the 6-month examination or experienced an IOL repositioning procedure (due to IOL misalignment during the study).

If a serious or device-related adverse event occurs at or prior to the 6-month visit, details of the event will be collected at the time of the event using an adverse event form. If the adverse event results in an IOL repositioning procedure due to misalignment, the questionnaire should be administered prior to the procedure to collect information regarding visual distortions. Keratometry and toric IOL axis measurements will be performed prior to the repositioning procedure to collect data regarding the IOL misalignment.

A chart summary of all examination procedures required at each study visit is provided in Appendix A.

## 11.2 VISIT SCHEDULE

The study visit schedule for all study subjects is outlined below in **Table 4**. Additional visits may be conducted at the discretion of the investigator; however routine follow-up visits without reports of serious or device-related adverse event(s) or spontaneous reports of visual distortion(s) are not considered study visits. Note that second-eye surgeries are intended to be performed within approximately 1 month ( $\leq 60$  days) of the first-eye surgery.

**TABLE 4**  
Study Visit Schedule

VISIT	EYES EVALUATED	EXAM	VISIT WINDOW
1	Both Eyes	Preoperative Exam	N/A
	First Eye Surgery		N/A
	Second Eye Surgery		Within approximately 1 month ( $\leq 60$ days) of 1 st eye surgery
2	Both Eyes	1 month	30-60 days postoperative from 2 nd implant
3	Both Eyes	6 months	120-180 days postoperative from 2 nd implant
4 a	Both Eyes	1 year a	330-420 days postoperative from 2 nd implant

a The 1-year exam is only required if a severe visual distortion was reported by the subject at the 6-month visit or if the subject underwent an IOL repositioning procedure during the study as a result of axis misalignment.

## 11.3 PREOPERATIVE PROCEDURES

All subjects enrolled in the study must sign the current IRB-approved informed consent document and meet the inclusion/exclusion criteria. The informed consent must be signed before any study-specific examinations are performed, and this must be documented in the source documents. An Authorization for Use/Disclosure of Health Information Form (HIPAA authorization) or similar medical treatment privacy law documentation must also be signed.

*As the Informed Consent Form is signed at the beginning of the preoperative study exam, some subjects may not qualify after study-specific testing is performed. Subjects will be considered screen-failures if they do not qualify or if they qualify but decide not to proceed with surgery. These subjects will be exited from the study.*

Study-specific preoperative testing for this protocol includes the administration of the subject questionnaire assessing visual distortions as well as any other preoperative procedures that are not already performed during the investigator's routine cataract evaluation for astigmatic patients (e.g., potential visual acuity). Documentation via the AMO Toric IOL Calculator options of toric power lens choice for each eye of each subject is required.

Preoperative testing to be performed for each eye includes the following:

- Informed consent documentation
- Subject demographic information
- Ocular history, including presence of ocular pathology for each eye
- Potential best-corrected distance visual acuity for each eye (Note: 20/30 or better is recommended for study inclusion; may be performed by surgeon estimation)
- Monocular uncorrected distance visual acuity (Snellen)
- Monocular best corrected distance visual acuity (Snellen)
- Manifest refraction (Snellen) for each eye
- Keratometry for each eye
- Intraocular pressure for each eye
- Ocular medications
- Cataract type and density for each eye
- Dilated fundus exam results for each eye (recommended)
- Medical and lens findings from a biomicroscopic slit-lamp exam for each eye
- Axial length, vertex distance, spherical equivalent IOL power and spherical equivalent targeted refraction (emmetropia, within  $\pm 0.50$  D) for each eye using the investigator's preferred biometry method
- A-constant used for spherical equivalent IOL power determination
- Surgeon-estimated surgically induced astigmatism (SIA) and planned incision location
- Documentation of the AMO Toric IOL Calculator choice of ZCT toric power for each eye and corresponding residual refractive cylinder and axis for each eye
  - Investigator to determine the most appropriate toric IOL model (ZCT450, ZCT525 or ZCT600 in at least one eye of each subject) based on the associated residual refractive cylinder (lowest) and axis
- Subject Questionnaire

**LENS POWER CALCULATIONS AND IOL SELECTION:**

For lens power calculations, the investigator's personalized A-Constant for the TECNIS Toric ZCT lens is to be used. The spherical equivalent lens power, as determined by the investigator's standard biometry methods, should be calculated to achieve emmetropia ( $\pm 0.50$  D) at distance for all eyes. Intentional overcorrection or under-correction (i.e., monovision or outside  $\pm 0.50$  D) should NOT be planned for either eye; however, surgeons may adjust the targeted refraction as necessary to achieve emmetropia based on their surgeon factor, study subject experience and/or subject first-eye outcomes.

In order to verify subject eligibility and to optimize toric IOL selection and axis placement, investigators will use the web-based AMO Toric IOL Calculator ([www.TecnisToricCalc.com](http://www.TecnisToricCalc.com)) to determine the appropriate TECNIS Toric IOL model for each eye (ZCT450, ZCT525 and/or ZCT600 must be implanted in at least one eye per subject for this study). Note that the AMO Toric IOL calculator provides toric IOL options based on predicted astigmatism, i.e., the vector sum of pre-existing corneal astigmatism and the expected effect of SIA. For this study, subjects are to have corneal astigmatism that, when taking SIA into account, have approximately 3.00 D to 4.75 D of predicted corneal astigmatism to be corrected and qualify for implantation of a ZCT450, ZCT525 and/or ZCT600 IOL in at least one eye (with the fellow eye also qualifying for implantation of ZCT300-ZCT600) as determined by the web-based AMO Toric IOL Calculator. Therefore, toric IOL calculations are to be performed for all subjects in this study and the toric IOL model selections chosen by the investigator via the AMO Toric IOL Calculator are to be printed and maintained as source documentation.

Note: Because lenticular astigmatism in the crystalline lens may influence the determination of the amount of astigmatism to be corrected, it is vital that corneal astigmatism (keratometry readings) and not refractive cylinder data be used for toric IOL calculations.

**11.4 STUDY LENS SUPPLY**

All lenses will be pulled from the site's own inventory and re-ordered per the standard practice at the site. Two lenses should be available for each case, a primary and a back-up lens.

**11.5 OPERATIVE PROCEDURES**

The investigator should use his or her standard, small-incision, phacoemulsification, cataract extraction surgical technique. Lenses should be folded for implantation and inserted into the capsular bag using one of the AMO-validated insertion systems. **No additional refractive procedures are to be performed during the operative**

**procedure or throughout the postoperative study period (e.g., LRI, OCCI, CRI, AK, PRK, LASIK or LASEK).**

Following lens insertion, the TECNIS Toric 1-Piece IOL is to be precisely aligned with the intended axis of placement using the imaginary line formed by the axis orientation marks at each of the haptic/optic junctions of the IOL, identifying the flat meridian of the optic. Carefully remove all viscoelastic from the capsular bag. Special care should be taken to ensure proper positioning of the TECNIS Toric IOL at the intended axis following viscoelastic removal and/or inflation of the capsular bag at the end of the surgical case. Residual viscoelastic and/or over-inflation of the bag may allow the lens to rotate, causing misalignment of the TECNIS Toric IOL from the intended axis.

Operative case report forms will include the following information:

- Date of surgery
- Operative eye
- IOL model, power and serial number
- Incision location
- Surgical complications
- Other surgical procedures
- IOL placement (e.g., within capsular bag, proper alignment, etc.)
- Wound closure (e.g., suture required)
- Adverse events

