## 6.2 OTHER ENDPOINTS

- Ratings of individual items included in the visual distortion questionnaire (PRVDQ)
- Mean percent reduction in absolute cylinder
- Mean refractive cylinder, mean refractive cylinder compared to intended, mean spherical equivalent and mean spherical equivalent compared to intended
- Percent of eyes with absolute cylinder within 0.50 D and within 1.00 D of intended
- Percent of eyes with spherical equivalent within 0.50 D and within 1.00 D of intended
- Uncorrected distance visual acuity (monocular and binocular)
- Best corrected distance visual acuity (monocular and binocular)
- Rates of medical and/or lens findings
- Rates of IOL repositioning procedures (secondary surgical intervention) due to IOL misalignment
- Mean difference between IOL axis marker location and postoperative steep keratometry meridian
- Rates of other adverse events

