## **12.3 ADVERSE EVENT AND COMPLAINT REPORTING REQUIREMENTS**

All adverse events and any complaint encountered using any AMO product, regardless of severity and whether or not attributed to the study device(s), are to be reported to AMO and recorded on the case report form corresponding to the visit during which awareness of the event occurred. All serious adverse events, whether anticipated or unanticipated, and all adverse device effects shall be reported using a serious or device related adverse event case report form and forwarded to AMO. Adverse events are also to be reported to the reviewing IRB as per the IRB's reporting requirements. If required, adverse events will be reported to the appropriate regulatory agencies (e.g., FDA) according to all applicable laws and regulations. Specific instructions on notification procedures to AMO are included in **Appendix D**, Adverse Event Reporting.

Reporting of adverse events shall follow the USA Code of Federal Regulations (21CFR812) for sites in the USA. General guidelines are provided below:

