#### **12.4 CAUSAL RELATIONSHIP**

The investigator should always be alert to adverse events that may be related to the study device or use of the study device (in the implantation procedure). An attempt should be made in every case to determine if the event may be device-related.

The following definitions are to be used as guidelines in determining the relationship between the event and the study devices: .

Definitely related:	There is a definite causal relationship between the adverse event and the device or implantation procedure.
Probably related:	There is a reasonable possibility of a causal relationship between the adverse event and the device or implantation procedure.
Possibly related:	The adverse event has not been determined to be related to the device or implantation procedure, but no other cause has been definitively identified and the device or implantation procedure cannot be ruled out as a possible cause.
Unlikely to be related:	The possibility of a potential causal relationship between adverse event and the device or implantation procedure could exist, but the adverse event is most likely explained by causes other than the device or implantation procedure.
Not related:	There is no possibility of a causal relationship between the adverse event and the device or implantation procedure.

If an adverse event is believed to be definitely, probably or possibly related to the study device, the event will be considered device-related.

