### **20.4 OTHER ENDPOINTS**

The frequency and proportion of subjects with each response will be reported for the individual visual distortion items on the visual distortion questionnaire for overall, with and without correction.

To evaluate if IOL axis misalignment changes are associated with severe visual distortions, descriptive statistics for IOL axis misalignment and mean difference between IOL axis marker location and postoperative steep keratometry meridian will be reported for subjects with and without severe visual distortions.

Descriptive statistics will be reported for mean percent reduction in cylinder, refractive cylinder, cylinder vs intended cylinder, spherical equivalent and spherical equivalent vs intended. The frequency and proportion of eyes within 0.50 D and within 1.00 D of intended values will be reported for refractive cylinder and spherical equivalent. The frequency and proportion achieving each acuity level will be reported for monocular and binocular uncorrected and best corrected distance visual acuity.

Enrollment data, demographic data, subject accountability data and operative complications/procedures will be reported using descriptive statistics. Visual distortion findings, adverse events and other key data will be reported at 1 year for subjects who experienced a repositioning procedure during the study or who were reported with severe visual distortions at the 6-month visit.

The frequency and proportion of subjects with medical/lens findings or adverse events will also be reported.

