### **3.3 Demographics/Preoperative/Operative Parameters**

Subject demographic data including age, sex, race, ethnicity and eye color will be presented. Age will be classified by less than 60, 60 to 69, 70 to 79, and equal to or older than 80 years old. In addition, mean age will be summarized with descriptive statistics. The frequency distributions of sex, race, ethnicity and iris color will also be tabulated.

The frequency and proportion of operative complications and additional operative procedures will be reported for primary and fellow eyes.

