### 4.4 Other Endpoints:

The mean percent reduction in cylinder will be reported for primary and fellow eyes at six months and will also be reported by IOL model. The percent reduction in cylinder is calculated for each eye using the following formula:.

$$100*((\text{Postop Ref. Cyl.} - \text{Preop K. Cyl.}) / (\text{Target Ref. Cyl.} - \text{Preop K. Cyl.}))$$

Key: Ref. Cyl.=absolute refractive cylinder; K. Cyl.=keratometric cylinder;

Refractive data will be referred to the corneal plane prior to determining percent reduction in cylinder.

To evaluate refractive predictability and refractive cylinder compared to intended, the mean absolute refractive cylinder, absolute refractive cylinder adjusted for the intended cylinder (i.e. target cylinder), spherical equivalent, and spherical equivalent adjusted for the intended spherical equivalent will be reported for primary and fellow eyes. The frequency and proportion of primary and fellow eyes within 0.5D and within 1.0D of intended values will be determined for refractive cylinder and spherical equivalent.

The frequency and proportion of primary and fellow eyes at each acuity line will be reported for monocular uncorrected and best corrected distance visual acuity at six months. Similar statistics will be reported for binocular visual acuity.

The frequency and proportion of medical and lens findings will also be reported for primary and fellow eyes. The frequency and proportion of adverse events at any time postoperative will also be reported for primary and fellow eyes for all subjects.

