Postop uncorrected distance visual acuity					
Postop corrected distance visual acuity					For ZCT300-ZCT400 pooled
Binocular visual acuity by acuity line level (No., percent)				x	
Postop uncorrected distance visual acuity					
Postop corrected distance visual acuity					
Medical and Lens Findings					
No. and percent with findings at 6 months	x	x			For ZCT450-ZCT600 pooled
					For ZCT300-ZCT400 pooled
Adverse Events					
No. and percent with adverse events at any time postoperative	x	x		x	For ZCT450-ZCT600 pooled and by IOL model
					For ZCT300-ZCT400 pooled

Key: Primary eyes=eye with the highest ZCT IOL (or first eye if the same IOL in both eyes),  
 SEQ=spherical equivalent, IOL group=subject assignment based on the highest ZCT IOL implanted  
 in either eye, x indicates tables will be provided, SD=standard deviation, Min=minimum,  
 Max=maximum, CI=Confidence interval, BCDVA=best corrected distance visual acuity,  
 UCDVA=uncorrected distance visual acuity

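### The only adverse-event rate the SAP specifies is limited to postoperative events, although adverse events are also collected at surgery and the protocol endpoint has no time limit

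*Protocol*

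**What the plan says.** **Collection.** Protocol Section 11.5 introduces the operative data with "Operative case report forms will include the following information". Surgical complications is one entry on the list that follows and adverse events is another. Appendix A marks adverse events for both operative visits. Section 12.3 covers events of any severity and attribution, and has them recorded on the form for the visit at which they became known. The relatedness categories in Section 12.4 take in the implantation procedure as well as the device.

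**Protocol endpoint.** Section 6.2 lists "Rates of other adverse events". Section 20.4 says "The frequency and proportion of subjects with medical/lens findings or adverse events will also be reported". Neither sets a time window.

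**SAP analysis.** Section 4.4 says "The frequency and proportion of adverse events at any time postoperative will also be reported for primary and fellow eyes for all subjects". The matching row of Appendix I reads "No. and percent with adverse events at any time postoperative". For surgery itself, Section 3.3 says "The frequency and proportion of operative complications and additional operative procedures will be reported for primary and fellow eyes", and Appendix I has one row for each of those two items. SAP Section 2.1 states that adverse events will be reported for all primary and fellow eyes in the study, with no time limit.

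**The concern.** The protocol treats an adverse event at surgery as something to record in its own right, apart from a surgical complication. The SAP then gives one adverse-event frequency, and its wording begins after surgery. A programmer working from Section 4.4 and Appendix I would have grounds to leave the operative form's adverse-event field out of the count, and would find no other table that uses it.

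This is a post-approval study whose stated purpose includes continued safety of the lenses. Events at implantation are close to the use of the device. Under Protocol Section 12.3 a serious or device-related event must reach the sponsor within 48 hours. If such an event happened during surgery, it could be in the safety reports and yet be missing from the final adverse-event table, and the two would then have to be reconciled.

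**Working it through.** The point rests mainly on wording, so the first step sets the places side by side.

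| Place | What it covers | Time window |
|---|---|---|
| Protocol 11.5 and Appendix A | Adverse events collected at each surgery, separate from complications | Includes surgery |
| Protocol 6.2 and 20.4 | Adverse-event endpoint and its analysis | None stated |
| SAP 2.1 | Adverse events for all primary and fellow eyes | None stated |
| SAP 4.4 and Appendix I | Adverse-event frequency and proportion | Postoperative only |
| SAP 3.3 and Appendix I | Operative complications and additional procedures, by eye | Surgery |

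**Step 1. Is the limit real or loose phrasing?** It appears in both places that define the output. SAP Section 4 is headed as postoperative analyses, and the Appendix I row sits in the postoperative block. The structure agrees with the wording. Against this, Section 2.1 has no limit, and the SAP does not define postoperative, so it is unclear whether the day of surgery counts.

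**Step 2. Where does each kind of intraoperative event go under a literal reading?**

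- Entered as a complication only: in the complications table.
- Entered as both a complication and an adverse event: in the complications table, not in the adverse-event rate.
- Entered as an adverse event only: in no assigned table.

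**Step 3. Size.** The plan has no figure for adverse events at surgery. Its one design figure, 86% in SAP Section 7, concerns the primary endpoint. It reproduces as P(X ≤ 3) = 0.859 for X ~ Binomial(80, 0.025), since the Clopper-Pearson half-width is 0.0490 at X = 3 and 0.0547 at X = 4. It does not depend on adverse-event counting.

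For scale only, take 80 bilateral subjects, hence 160 eyes, and assume a rate p per eye for an intraoperative event of any kind. Treat eyes as independent. The expected number is 160p, and the chance of at least one is 1 − (1 − p)^160.

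| Assumed p | Expected events | Chance of at least one |
|---|---|---|
| 0.5% | 0.8 | 55% |
| 1% | 1.6 | 80% |
| 3% | 4.8 | 99% |

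These rates are assumptions. They cover all three routes in Step 2, so at a given p they overstate the number of events with no table.

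The effect on a reported rate is simpler. One subject in 80 is 1/80 = 1.25 percentage points; one eye in 160 is 1/160 = 0.625 points. If 0 to 5 subjects each had one adverse event at surgery and none later, leaving those events out would lower the subject-level rate by 0 to 5 × 1.25 = 6.25 points.

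**The case against.** The best defence is that little would go unreported. Operative complications are tabulated by eye under SAP Section 3.3, and Protocol Section 20.4 also commits to reporting them. Showing events at surgery apart from later events is a reasonable layout. The serious events anticipated in Protocol Section 12.1 are mostly postoperative by nature. Serious and device-related events also reach the sponsor and the medical monitor directly, and the interim safety summaries in Section 20.5 have no postoperative limit. SAP Section 2.1 can be read as promising complete adverse-event reporting, and no sentence says that operative-form adverse events are excluded.

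Much of this stands. A reader might infer that events during implantation vanish from the study's results. The documents do not support that, because the complications table remains. A reader might also take 55%, 80% or 99% as the chance that an event is omitted from all reporting. That does not follow either: those figures rest on assumed rates of any intraoperative event, many of which would be in the complications table, and both eyes of one subject are unlikely to be independent.

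Two things survive. Section 2.1 says which eyes are reported, whereas Section 4.4 and Appendix I specify the actual frequency, so the unlimited sentence leaves an inconsistency to resolve. And the complications table is planned as counts of responses to a different field; nothing says that operative-form adverse events are carried into it.

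**Conclusion.** The point holds in a limited form. The only adverse-event frequency that the SAP specifies has a narrower window than the protocol endpoint and conflicts with SAP Section 2.1. On a literal reading, an adverse event entered at surgery is outside that rate, and one not also entered as a complication has no assigned table.

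The number of events in that last group cannot be derived from the documents and may be small or zero. This conclusion assumes that the SAP means what Section 4.4 and Appendix I say and that postoperative does not include the operation. If the sponsor intends the day of surgery to count, the defect is one of definition only. The analysis concerned is descriptive; the primary endpoint and the sample size are untouched.

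**What to change.** In SAP Section 4.4 and the adverse-event row of Appendix I, replace the postoperative limit with: *at any time from the start of that eye's surgery, including intraoperative events*. Show an intraoperative line, a postoperative line and a total. Keep the surgical-complications table. State that an event entered in both operative-form fields is counted once in the adverse-event total.

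The window should start at each eye's own surgery, because the table is by eye and the second surgery may follow the first by up to 60 days. A single start at the first surgery would charge the second eye with events before its implantation.

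The data are already on the operative form. The cost is a change of SAP wording, one extra table line, and possibly a slightly higher reported adverse-event rate.
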